1.2 Dose Rationale

In this study, belimumab will be administered as 10 mg/kg IV infusions dosed at the same frequency as in the current labeling for SLE.

The selection of belimumab dose was based on review of pooled analyses of safety, efficacy and pharmacokinetic (PK) data from Phase 3 SLE studies. In those studies,

not only for the primary endpoint, but also for some disease activity and flare indices, and for certain critical biomarkers (anti-double-stranded deoxyribonucleic acid (dsDNA) antibodies, complement levels and B-cell subsets), a dose response relationship was seen, with greater differences from placebo for the belimumab 10 mg/kg group than the belimumab 1 mg/kg group. The differences were more marked when only data from subjects with low complement and anti-dsDNA at baseline were analyzed ¹⁴.

In transplantation, unlike SLE or other autoimmune diseases, the event (reperfusion of the allograft) that triggers the pathogenic process is easily identified. In this study, to maximize BLyS binding at the time of this triggering event, the first dose of investigational product will be administered on the day of transplantation intraoperatively. Where possible, study drug infusion should be completed before reperfusion of the allograft.

This study will focus on examining the impact of belimumab during the first 6 months after transplantation, when episodes of rejection are most likely to occur; investigational product will be administered at Day 0, Week 2, Week 4 and then every 4 weeks through Week 20. Subjects will then be observed through the 1-year study period with no further belimumab dosing.

For detailed information of the safety and efficacy of belimumab at each of the doses studied, refer to the IB GlaxoSmithKline Document Number 2011N128591_01 (Investigator's Brochure: Belimumab. Version 11: 20-JUN-2013: always refer to the most recent version).

1.3 Summary of Known and Potential Risks and Benefits to Human Subjects

Belimumab: Belimumab has been generally well tolerated in the Phase 2 and Phase 3 SLE studies. The majority of subjects in the SLE studies were receiving concomitant corticosteroids and/or other immunosuppressants including azathioprine and mycophenolate mofetil (MMF). Precautions will be taken to mitigate the risk of infections, infusion and hypersensitivity reactions, and the potential risk of malignancy. These precautions will include the use of the ICTR Data Monitoring Committee (DMC), which will review subject safety and efficacy data.

Common adverse reactions ($\geq 5\%$) in clinical trials were: nausea, diarrhea, pyrexia, nasopharyngitis, bronchitis, insomnia, pain in extremity, depression, migraine, and pharyngitis. Serious adverse reactions have included: infections, Progressive Multifocal Leukoencephalopathy (PML), Hypersensitivity reactions; including anaphylaxis, depression. .

PML

Progressive multifocal leukoencephalopathy (PML) resulting in neurological deficits, including fatal cases, has been reported in SLE patients receiving immunosuppressant pharmacotherapy, including belimumab. A diagnosis of PML should be considered in any subject presenting with new-onset or deteriorating neurological signs and symptoms. The subject should be referred to a neurologist or other appropriate specialist for evaluation. If PML is confirmed, study agent should be discontinued and consideration should be given to stopping immunosuppressant therapy.

If PML is suspected, this should be immediately reported to the Medical Monitor. The appropriateness of continuing study agent, while the case is being assessed, should be discussed.

Suicidality

Some autoimmune diseases have an increased risk of suicidal behavior and/or ideation [Bachen, 2009; Timonen, 2003; Stenager, 1992]. For this reason in studies of patients with autoimmune disease, patients should be clinically assessed for suicidal ideation and/or behavior at each visit, but not for study purposes. If patient exhibits suicidal ideations or it is verbally expressed, the PI will enter a note and refer the patient to a psychiatrist.

Dosing

Infusion reactions occurred more frequently on the first two infusion days and tended to decrease with subsequent infusions. Delay in the onset of acute hypersensitivity reactions has been observed and recurrence of clinically significant reactions after initial resolution of symptoms following appropriate treatment, have been observed. Therefore, patients should remain under clinical supervision for 3 hours after completion of the first 2 IV infusions. Should symptoms of acute hypersensitivity occur, an extended period of monitoring may be appropriate, based on clinical judgment. This may include, but is not limited to, monitoring vital signs and observing any untoward reactions. Beyond the first 2 IV infusions, subjects should be monitored during and for an appropriate period of time after administration according to the study sites' guidelines or standard operating procedure for IV infusions. Patients treated with belimumab should be made aware of the potential risk, the signs and symptoms of such reactions, and the importance of immediately seeking medical attention. Delayed-type, non-acute hypersensitivity reactions have also been observed and included symptoms such as rash, nausea, fatigue, myalgia, headache, and facial oedema.

For additional information on the risks associated with belimumab, refer to the package insert for Benlysta® (GlaxoSmithKlein) at:
https://www.gsksource.com/pharma/content/dam/GlaxoSmithKline/US/en/Prescribing_Information/Benlysta/pdf/BENLYSTA-PI-MG.PDF

In this study, belimumab will be administered in combination with standard of care immunosuppressants, which will include alemtuzumab, tacrolimus, mycophenolic acid and corticosteroids (standard taper) for all study subjects. There has been no experience with the use of alemtuzumab or tacrolimus in combination with belimumab, while there are data on the use of belimumab in combination with MMF and/or corticosteroids. As with all immunosuppressants, each of these agents has the potential to be associated with infections and/or malignancy.

Alemtuzumab: The most common adverse events associated with alemtuzumab are:

- Infusion reactions including moderate fever and chills
- Leukopenia

As with all immunosuppression, administration of alemtuzumab may be associated with an increased risk of infection and the development of malignancy (especially of the skin and lymphoid system). Alemtuzumab (30 mg IV x 1) is standard induction immunosuppression for both cadaveric and living-donor renal transplants at many centers.

In 251 kidney-transplant recipients receiving alemtuzumab induction (30 mg IV x 1), the adverse events did not differ significantly between patients treated with alemtuzumab, anti-thymocyte globulin and basiliximab. The principal side effects were leucopenia (57%) and infection (32%). CMV infection occurred in 13% of the recipients and PTLD in two of the recipients.

The carcinogenic effects and the effect of alemtuzumab on fertility have not been established. Alemtuzumab is contraindicated in patients who have active acute or chronic infections that contraindicate any additional immunosuppression.

For additional information on the risks associated with alemtuzumab, refer to the package insert for Campath® (Genzyme Corporation) at the following website:
<http://www.campath.com/pdfs/2009-08-Campath%20US%20PI.pdf>

Tacrolimus: The following risks are associated with the administration of tacrolimus:

- Hypertension.
- Hyperkalemia.
- Nephrotoxicity.
- Neurotoxicity.
- Post-transplant insulin-independent diabetes mellitus.
- Myocardial hypertrophy (in most cases reversible upon dose reduction).
- Increased risk of renal insufficiency in patients with hepatic impairment.
- Increased susceptibility to infection.

For additional information on the risks of tacrolimus, refer to the Prograf® package insert at the following website: <http://www.astellas.us/docs/prograf.pdf>.

Mycophenolic Acid: The following risks are associated with the use of mycophenolic acid are:

- Increased risk of developing lymphomas, lymphoproliferative diseases and other malignancies especially of the skin in patients receiving MMF as part of an immunosuppressive regimen. The risk appears to be related to the intensity and duration of immunosuppression rather than to the use of any specific agent.
- Increased susceptibility to infection, including opportunistic infections, fatal infections and sepsis.
- Increased risk of developing latent viral infections including Progressive Multifocal Leukoencephalopathy (PML) and BK virus- associated nephropathy.
- Increased risk of first trimester pregnancy loss and congenital malformations, especially of the external ear, face, limbs, heart esophagus and kidneys.
- Increased risk of neutropenia and leukopenia
- Increased risk of gastrointestinal bleeding.

Common side effects associated with use of MMF include diarrhea, abdominal pain, nausea and vomiting, headache and drug induced fever.

For additional information about the risks of mycophenolic acid, refer to the Myfortic® package insert at the following website:
<http://www.pharma.us.novartis.com/product/pi/pdf/myfortic.pdf>

Dexamethasone: Side effects of dexamethasone include convulsions, headache, vertigo, mood swings, psychosis, congestive heart failure (CHF), hypertension, salt and water retention, increased potassium excretion, Cushing syndrome, menstrual irregularities, hyperglycemia, GI irritation, peptic ulcer, weight gain. Dermatologic effects may include thin skin, petechiae, ecchymosis, facial erythema, poor wound healing, hirsutism and urticaria. Muscle weakness, loss of muscle mass and osteoporosis may also occur. Ophthalmologic complications may include increased intraocular pressure, glaucoma, exophthalmos and cataracts. Other complications may include immunosuppression and increased susceptibility to infection.

For further information about the risks associated with dexamethasone, please refer to the package insert at the following website:

<http://www.americanregent.com/documents/Product15PrescribingInformation.pdf>

2. Objectives

We propose an open-label, single-arm, pilot study to test whether the addition of belimumab, to inhibit the B cell survival factor BLyS at the time of kidney transplantation, to standard of care therapy (alemtuzumab and steroid induction with mycophenolic acid and tacrolimus maintenance immunosuppression) will prevent the generation of de novo DSA.

3. Study Design

3.1 Description

We propose an open-label, single-arm pilot study to examine the addition of belimumab at induction to our standard of care regimen of alemtuzumab and steroid induction followed by tacrolimus and mycophenolic acid maintenance immunosuppression in adult living donor kidney transplant recipients to assess its ability to induce functional B-cell transplant tolerance: prevent the generation of de novo DSA. Significant support for this hypothesis exists in the literature including 1) the successful induction of transplant tolerance in a preclinical model [9], 2) the transitional B cell tolerance signature [11] 3) the association of elevated BLyS levels with the development of de novo DSA post kidney transplant [2, 12, 13]. Our study population will consist of sensitized adult kidney transplant recipients: PRA>0 and/or sum DSA<1000 MFI. The primary endpoint of this study is de novo DSA production.

There are two main reasons for selecting this patient population for our proposed study. 1) Sensitized patients are known to have higher rates of de novo DSA production and 2) excluding patients with lower levels of DSA (sum DSA<1000 MFI) will enable more fidelity in determining the DSA that is produced *de novo*.

Additionally, we contend that alemtuzumab should be the induction agent of choice for this study instead of Thymoglobulin for three reasons. 1) In the United States it is provided at no cost and is easy to administer (a single 30mg dose is given

intravenously with no central venous access required). This cuts down significantly on cost as opposed to Thymoglobulin. 2) Mechanistically, more support exists in the literature for the use of alemtuzumab rather than Thymoglobulin. BLyS levels have been shown to significantly increase after alemtuzumab induction as opposed to Thymoglobulin induction, and lastly, 3) *de novo* DSA production appears to be ~50% at 2 years with alemtuzumab (potentially due to the increase BLyS levels). Therefore, we are potentially more likely to show a reduction in DSA levels (the primary endpoint) compared to our control cohort.

We will collect blood samples prior to transplant, then 1, 3, 6, 9 and 12 months to measure anti-HLA antibodies and BAFF/APRIL levels. In addition, we will collect protocol kidney biopsies at time of transplant and at 1-year post transplant.

3.2 Study Endpoints

3.2.1 Primary Endpoints

The primary endpoint of this study is *de novo* DSA production at 1, 3, 6, 9, and 12 months.

3.2.2 Secondary Endpoints

Secondary endpoints will be 1) graft survival and function as determined by serum creatinine/eGFR and urine protein at 1, 3, 6, 9, and 12 months 2) rates of acute cellular and antibody mediated rejection at 1, 3, 6, 9, and 12 months and 3) the nature, frequency, and severity of serious and non-serious adverse events \geq Grade 2.

3.3 Study Population

Subjects 18-60 years of age receiving a living donor kidney transplant who are sensitized by pregnancy, transfusions, or prior transplant: PRA>0% and/or sum DSA<1000 MFI.

3.4 Screening and Enrollment

This research study will be explained in lay language to each potential research participant. The participant will sign an informed consent prior to any screening study procedures. After written consent is obtained, subjects who are deemed to qualify for the study will be enrolled. Potential subjects will be invited to participate initially via phone or in person by study personnel to briefly explain the study. If the potential subject agrees, the study personnel will go through the consent form and answer questions. The study personnel will ask the potential subject if they would like to be in the study. If the subject agrees to participate, they will be informed about signing the consent and setting up study visits.

3.5 Criteria for Discontinuation

It is understood by all concerned that an excessive rate of withdrawals can render the study uninterpretable; therefore, unnecessary withdrawal of subjects should be avoided.

In addition to the reasons for withdrawal provided below, subjects are free to withdraw from treatment or from the study at any time for any reason or may be withdrawn if necessary to protect their health.

Subjects who withdraw from the study or study treatment after receiving at least one dose of investigational product will continue to be followed up until the end of the study.

Reasons for withdrawal may include the following:

- Prohibited concurrent medication or therapy
- **Prior therapy at any time:** has ever received any of the following: B-cell targeted therapy (e.g., rituximab, other anti-CD20 agents, anti-CD2 [epratuzumab], anti-CD52 [alemtuzumab], BLyS-receptor fusion protein [BR3], TACI fragment, crystallizable (Fc), or belimumab)
- Live vaccines within 30 days
- Unacceptable toxicity as assessed by the PI

Study drug must be discontinued if the investigator determines that continuing it would result in a significant safety risk for that patient. Subjects MUST discontinue investigational product for any of the following reasons:

- Withdrawal of informed consent (subject's decision to withdraw for any reason).
- Any clinical adverse event, clinically significant laboratory abnormality, or concurrent illness, which, in the opinion of the investigator, indicates that continued participation in the study is not in the best interest of the subject.
- Pregnancy - Instruct WOCBP (Women of Child Bearing Potential) to contact the investigator or study staff immediately if they suspect they might be pregnant (e.g., missed or late menstrual period) at any time during study participation. The investigator must immediately notify GlaxoSmithKline if a study subject becomes pregnant. The pregnancy must be followed up to determine outcome (including premature termination) and status of mother and child. Pregnancy complications and elective terminations for medical reasons must be reported as an AE or SAE. Spontaneous abortions must be reported as an SAE. Any SAE occurring in association with a pregnancy brought to the investigator's attention after the subject has completed the study and considered by the investigator as possibly related to the study treatment, must be reported to GSK within 24 hours.
- Loss of ability to freely provide consent through imprisonment or involuntary incarceration for treatment of either a psychiatric or physical (e.g., infectious disease) illness.
- AE(s) (including infections, abnormal laboratory value(s), abnormal test procedure result(s) including ECG abnormalities, unsatisfactory death, significant protocol deviation, withdrawal of consent, or lost to follow-up, according to the criteria specified above.
- Malignancy (except non-melanoma skin cancer)

In addition to these requirements for study drug discontinuation, the investigator should discontinue study drug for a given patient if, in his/her professional judgment, it is felt that continuation would be detrimental to the patient's well-being.

Patients may withdraw from the study for any reason at any time.

All subjects who discontinue should comply with any protocol-specified follow-up procedures. The only exception to this requirement is when a subject withdraws consent for all study procedures or loses the ability to consent freely (i.e., is imprisoned

or involuntarily incarcerated for the treatment of either a psychiatric or physical illness). If a subject withdraws before completing the study, the reason for withdrawal must be documented appropriately.

3.5.1 Discontinuation of study treatment and premature patient withdrawal

Patients may voluntarily withdraw from the study treatment or from the study for any reason at any time. They may be considered withdrawn from the study if they state an intention to withdraw, fail to return for visits, or become lost to follow-up for any other reason. If premature withdrawal occurs for any reason, the investigator must make every effort to determine the primary reason for a patient's premature withdrawal from the study. The investigator should discontinue study treatment for a given patient or withdraw the patient from study if, on balance, he/she believes that continuation would be detrimental to the patient's well-being. Patients who discontinue study treatment should NOT be considered withdrawn from the study and should continue to be followed until the end of the study, unless consent is withdrawn. Patients who are prematurely withdrawn from the study will not be replaced by an equal number of newly enrolled patients.

3.6 Criteria for Terminating the Study

The Principal Investigator will review safety and efficacy criteria on an ongoing basis. The study enrollment will be halted and data reviewed by the Data Safety Monitoring Committee and the University of Wisconsin Health Sciences Institutional Review Board for any of the following:

- 1) If greater than two patients are discontinued from study treatment due to elevated liver function tests as described in the protocol.
- 2) If greater than two patients develop hypogammaglobulinemia and infectious complications resulting in discontinuation of study treatment
- 3) Death of one or more patients.

After this review, the Investigator, Data Safety Monitoring Committee and the IRB will jointly make a final determination regarding continuation, modification, or termination of the study. The study can be terminated at any time for any reason by the Principle Investigator or GlaxoSmithKline, Inc. Should this be necessary, the patient should be seen as soon as possible. The investigator may be informed of additional procedures to be followed in order to ensure that adequate consideration is given to the protection of the patient's interests. The investigator will be responsible for informing the DMC, IRB and the FDA of the early termination of the trial.

See Section 7.3 for information on the ICTR Data Monitoring Committee (DMC) for this study.

4. Selection of Subjects

Potential subjects will be identified prior to kidney transplant based on the following inclusion and exclusion criteria.

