5.1.2 Treatment monitoring and dose modifying strategies

The following AEs, laboratory assessment results or changes in concurrent medications require evaluation and discussion with the GSK medical monitor within 24 hours of the investigator becoming aware of the event.

Dose Adjustment and Discontinuation

If a subject experiences a clinically significant AE and this AE continues at the next scheduled dose, or could potentially be exacerbated by the next dose, the investigator may delay the next dose by up to 2 weeks or withhold 1 dose, per physician discretion. As a result, any subsequent study visits will be adjusted. If a similar concern is present at the time of the next scheduled dose, any decision made to discontinue treatment will be driven by the Investigator's clinical judgment. Laboratory tests will be repeated per Investigator's discretion.

If it is determined that investigational product should be discontinued, the subject should be followed at regularly scheduled monthly study visits as required until resolution of the AE, and return for follow-up visits as described in Subject Withdrawal Criteria.

For a full listing of the discontinuation criteria, please see section 3.5 of the protocol.

Hypogammaglobulinemia

Benlysta should be discontinued in subjects with IgG levels <250 mg/dL associated with a severe or serious infection. For IgG concentrations < 250 mg/dL that are not associated with a severe or serious infection, increased vigilance for infection is required. Clinical judgment should be applied with respect to the appropriateness of continuing study therapy in these subjects. If a subject experiences any IgG levels < 250 mg/dL, the dose of study agent must be withheld and the Medical Monitor and GlaxoSmithKlein must be consulted before administering any subsequent dose of study agent. If a subject experiences a clinically significant, potentially life-threatening (Grade 4) AE that the investigator believes may be definitely, possibly or probably related to study agent, then treatment with study agent will be discontinued. The subject should be withdrawn from study agent, and followed at regularly scheduled study visits as specified by protocol and also until resolution of the AE(s) (whichever is longer).

Liver Chemistry Stopping Criteria

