Grade 3 Severe or medically significant but not immediately life-threatening; hospitalization or prolongation of hospitalization indicated; disabling; limiting self care ADL

Grade 4 Life-threatening consequences; urgent intervention indicated.

Grade 5 Death related to AE.

7.2 *Serious Adverse Events*

A Serious Adverse Event (SAE) is any untoward medical occurrence that at any dose:

- Is fatal
- Is life-threatening
- Requires or prolongs inpatient hospitalization
- Results in persistent or significant disability/incapacity
- Is a congenital anomaly/birth defect

The inpatient stay following the transplantation procedure will be considered SAE only if prolonged for more than 14 days.

A medical event that may not be immediately life-threatening or result in death or hospitalization but may jeopardize the subject or may require intervention to prevent a serious outcome, may also be considered serious (e.g. intensive treatment in an emergency room or at home for allergic bronchospasm; blood dyscrasias or convulsions that do not result in hospitalization; or development of drug dependency or drug abuse). Medical and scientific judgment must be exercised when classifying events as serious. The Investigator must determine both the intensity of the serious adverse event and the relationship of the event to the administration of study medications.

7.2.1 *Reporting*

It is the responsibility of the Investigator to promptly notify the Institutional Review Board of all unanticipated problems involving risk to human research subjects. All serious adverse events including fatal or life-threatening events experienced by study participants in the study will be reported to GlaxoSmithKline, Inc., to ICTR DMC, the FDA per applicable regulations, and the UW IRB according to current IRB guidelines.

Adverse Events that are:	Notify:
Serious Suspected/Related* Unexpected	GSK Medical Monitor: Within 24 hours DMC: Within 14 business days HSIRB: Within 14 business days FDA and all participating institutions as soon as possible, but no later than 15 calendar days after learning of the event
Life threatening or Fatal Suspected/Related* Unexpected	GSK Medical Monitor: Within 24 hours DMC: Within 24 hours HSIRB: Within 1 business day of learning of the event. FDA: Within 7 calendar days of learning of the event
*Events that are possibly, probably, or definitely related meet the criteria for "Suspected/Related"	

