7.3 **ICTR Data Monitoring Committee (DMC)**

We plan to utilize the UW ICTR Data Monitoring Committee (DMC) to oversee the study. The UW ICTR DMC is comprised of experienced members (core plus ad hoc) with expertise required to oversee this study. The DMC members will review protocol-specific reports created by statisticians using data pulled from the ICTR OnCore clinical research management system and Research Electronic Data Capture (REDCap) data management tool. These standard reports will include an overview of study objectives, a review of actual and projected accrual rates, an evaluation of patient demographics for balance of randomization, and a summary of the number and seriousness of adverse events. An interim analysis of study results may be performed and source documents may be reviewed to allow the DMC to independently judge whether the overall integrity and conduct of the protocol remain acceptable based on data provided and reported by the Principal Investigator. The DMC will make recommendations to the Principal Investigator that could include actions of continuation, modification, suspension, or termination.

In providing oversight for the conduct of this study, the ICTR DMC will meet biannually during the study to review all adverse events. Additional meetings may be scheduled as determined by the DMC or as requested by the PI. The predefined stopping points for this study are described in section 3.6 of this protocol. We will submit all reportable events to the DMC and the Health Sciences IRB in accordance with their reporting guidelines.

8. Ethical Considerations and Compliance in Good Clinical Practice

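### After a death, Section 3.6 automatically halts only enrollment: subjects already on belimumab get no interim hold, and the review has no deadline

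*Combined protocol and SAP*

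**What the plan says.** Section 3.6 lists three triggers: more than two subjects taken off treatment for raised liver tests, more than two taken off for hypogammaglobulinemia with infection, and one or more deaths. On any of them, "The study enrollment will be halted and data reviewed by the Data Safety Monitoring Committee" and by the IRB. The investigator, the committee and the IRB then decide jointly whether the study continues, changes or ends. Doses still due in enrolled subjects are not mentioned, and no time limit is given. The section adds that "The study can be terminated at any time for any reason by the Principle Investigator or GlaxoSmithKline, Inc".

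Other sections bear on the same situation:

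- **Section 3.5:** "Study drug must be discontinued if the investigator determines that continuing it would result in a significant safety risk for that patient".
- **Section 5.1.2:** for a subject's own continuing adverse event, "the investigator may delay the next dose by up to 2 weeks or withhold 1 dose, per physician discretion". An IgG below 250 mg/dL requires that subject's dose to be withheld and the Medical Monitor and GSK consulted before any later dose.
- **Section 7 (opening text):** every SAE goes to GSK within 24 hours.
- **Section 7.2.1:** all SAEs go to the DMC, but the 24-hour DMC limit is in the table row for events that are "Life threatening or Fatal Suspected/Related* Unexpected".
- **Section 7.3:** the DMC meets biannually, may recommend suspension, and treats Section 3.6 as the stopping points. "Additional meetings may be scheduled as determined by the DMC or as requested by the PI".

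**The concern.** A halt to enrollment protects people who have not yet joined. After a death in a 5-subject study, those most in need of protection are the other subjects still receiving infusions to Week 20. Section 3.6 gives them no automatic pause, and with no deadline the review could run past one or more of their doses. If all 5 are already enrolled, the halt changes nothing and dosing is the only thing left to pause.

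Two features of this trial make that matter. Section 1.3 states that belimumab has not been used before with alemtuzumab or tacrolimus, and every subject receives both. Belimumab is also an add-on, so it can be held briefly while the immunosuppression that protects the graft continues.

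**Working it through.** The plan states no figure on this point, so there is none to reproduce. The check has two parts: a search for any rule that fills the gap, and a count of the doses at stake.

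**1. Is there a study-level hold or a review deadline elsewhere?**

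| Place | What it supplies | Set off automatically for other subjects by a 3.6 trigger? |
|---|---|---|
| 3.5 | Mandatory stop once the investigator finds a significant risk for that patient | No; needs a finding |
| 3.6 | Termination by the investigator or GSK | No; discretionary |
| 5.1.2 | Delay, hold and stopping rules | No; tied to the subject's own event |
| 7 and 7.2.1 | Notification times | Sets when parties are told, not when a review ends |
| 7.3 | Optional extra meetings; possible recommendation to suspend | The case reaches the DMC, but no hold and no deadline follow |

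None of these provides an interim hold or a review deadline.

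**2. How many others can be on drug?** After one death, 5 − 1 = 4. Criteria 1 and 2 each need at least 3 subjects already off treatment, so 5 − 3 = 2 at most.

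**3. Doses due per subject on treatment.** The schedule is weeks 0, 2, 4, 8, 12, 16 and 20, which gives intervals of 2, 2, 4, 4, 4 and 4 weeks. Assume the trigger falls uniformly over the 20 weeks and the review lasts L weeks (assumed; the plan gives no length).

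- L = 1: 6 × 1/20 = 0.30 doses on average, range 0 to 1.
- L = 2: 6 × 2/20 = 0.60, range 0 to 1.
- L = 4: at least one dose always falls due, and two do if the trigger is in the first 2 weeks, so 1 + 2/20 = 1.10, range 1 to 2.
- Wait to the subject's own next dose: for w up to 2 weeks, P(wait ≤ w) = 6w/20. Setting this to 0.5 gives a median of 1.67 weeks. P(wait > 2) = 4 × 2/20 = 0.40.

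**4. Doses due across all survivors.** Assume the five subjects start at 0, d, 2d, 3d and 4d weeks. One of them, equally likely, dies at a uniform time in the first W weeks of its own follow-up, and the review takes 4 weeks. Count doses due in subjects who have started and are not past Week 20. W = 20 is the dosing period and W = 52 the full follow-up.

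| | d = 2 | d = 4 | d = 8 | d = 12 |
|---|---|---|---|---|
| Mean doses, W = 20 | 3.4 | 2.6 | 1.3 | 0.7 |
| No other subject on treatment, W = 20 | 4% | 8% | 16% | 36% |
| All 5 started, a survivor still has doses due, W = 20 | 78% | 56% | 28% | 16% |
| Mean doses, W = 52 | 1.5 | 1.3 | 1.1 | 0.9 |
| No other subject on treatment, W = 52 | 55% | 49% | 37% | 37% |
| All 5 started, a survivor still has doses due, W = 52 | 38% | 37% | 35% | 26% |

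The third and sixth rows show how often the halt stops nothing while a pause in dosing still could. They are conservative, because a subject is enrolled before starting drug.

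**5. How fast must a review be to cost no dose?** In the same model with W = 20 and at least one survivor on treatment, the median wait to the next dose of any subject is 1.0 week at d = 2 and 1.4 to 1.6 weeks at d = 4 to 12. It is under 1 week in 49% and in 31 to 36% of cases respectively.

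**The case against.** The strongest reply is that the protocol is not short of people able to stop dosing. GSK learns of every SAE within 24 hours, whatever the cause, and can end the study. The investigator reviews safety continuously and must stop drug on finding a significant risk. A 3.6 trigger itself brings in the DMC, which can recommend suspension. Related events include those judged possibly related, so deaths outside the 24-hour DMC row are the unrelated or expected ones, where a hold in others is least needed. In a 5-subject study, leaving the interim decision to the investigator is a defensible choice.

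Much of this stands. A reader might infer that the protocol permits infusions to go on after a death, or that nobody could stop them. The documents support neither: Section 3.6 is silent on dosing, and several parties have the power to stop it. A reader might also infer that deaths outside the 24-hour row need not reach the DMC. Section 7.2.1 sends it all SAEs, and Section 7.3 points to the DMC's own reporting guidelines, which are not reproduced; only the time limit is unstated here.

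What remains is that every one of these routes needs someone to act, and the one automatic action may protect nobody. The protocol already accepts hold-then-consult for a low IgG in a single subject. A short hold after a death applies the same logic to the others.

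A reader might want the hold to cover all three criteria and to bar new starts as well. That goes too far. Criteria 1 and 2 leave at most 2 subjects, who are covered by the individual stopping rules in Section 5.1.2. Barring a start would cost a subject the intraoperative dose intended "to maximize BLyS binding at the time of this triggering event", and Section 3.5.1 says "Patients who are prematurely withdrawn from the study will not be replaced by an equal number of newly enrolled patients".

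**Conclusion.** The point holds as a gap in automatic protection, mainly for the death trigger. When a 3.6 criterion is met, the written rule halts enrollment and starts a review without a deadline; it does not pause belimumab in subjects on treatment. It is not an absence of dosing safeguards, because discretionary ones exist and GSK is told of every death quickly.

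The size is modest but real: up to 4 other subjects on drug, and a mean of 0.6 or 1.1 doses per treated subject for an assumed 2- or 4-week review. These figures rest on assumed review length, accrual spacing and timing of death. They are conditional on a death; the plan gives no probability of one, so the expected impact is unknown. Over 52 weeks, no other subject is on treatment in 37% to 55% of modelled deaths. The change should be made, since it is cheap and the combination is untested, but the study does not fail without it.

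**What to change.** Add to Section 3.6, for the death trigger only:

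> The investigator notifies the DMC of any death within 24 hours, whatever the cause, and requests an ad hoc review at once (which may be by its chair). The next belimumab dose of each subject on treatment is held until the investigator and the DMC have documented a decision to continue; the review is targeted before the next scheduled dose. Standard of care immunosuppression continues, and the joint determination with the IRB follows as written.

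Starts in enrolled subjects not yet transplanted are left to the investigator and the DMC.

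The change needs a few sentences and the DMC's agreement to an ad hoc review, which Section 7.3 already allows. It adds no patients, visits or procedures.

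The downside is that a late review delays or omits maintenance doses, at the per-subject means given above. A subject in the first 2 weeks of treatment could miss 2 doses in a 4-week review, more than the single withheld dose in Section 5.1.2. Avoiding any missed dose may require a decision within about a week, which is why the text sets a target and allows review by the chair.
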